## STATEMENT OF COMPLIANCE

The trial will be carried out in accordance with International Council on Harmonisation Good Clinical Practice (ICH GCP) and the following:

- United States (US) Code of Federal Regulations (CFR) applicable to clinical studies (45 CFR Part 46, 21 CFR Part 50, 21 CFR Part 56, 21 CFR Part 312, and/or 21 CFR Part 812).

National Institutes of Health (NIH)-funded investigators and clinical trial site staff who are responsible for the conduct, management, or oversight of NIH-funded clinical trials have completed Human Subjects Protection and ICH GCP Training.

## 1 PROTOCOL SUMMARY

### 1.1 SYNOPSIS

Title:	Health Literacy and Obesogenic Behaviors
Grant Number:	R21DK117345
Study Description:	The goal of the proposed study is to examine the effect of adding a health literacy component to an obesity prevention intervention that addresses adolescents' obesogenic behavior-related health knowledge, motivation, and behavioral skills. The central hypothesis is adolescents receiving health literacy training as part of an obesity prevention intervention will have higher rates of prevention behaviors than those in the obesity prevention only condition.
Objectives*:	Primary Objective: Determine if the addition of HL training to an interactive digital obesity prevention intervention will improve adolescents' obesity prevention behaviors over the obesity intervention alone.
Endpoints*:	Primary Endpoint: 1-month follow-up
Study Population:	Adolescents
Phase* or Stage:	Phase 1
Description of Sites/Facilities Enrolling Participants:	Community sites in the United States
Description of Study Intervention/Experimental Manipulation:	Web-based intervention administered to individuals. The intervention contains 5 modules with an expected completion rate of 1 module per week.
Study Duration*:	5 months
Participant Duration:	3 months

### 1.2 SCHEDULE OF ACTIVITIES

	Week 1	Week 2	Weeks 3-7	Week 8	Week 12
Parent permission	X				
Adolescent assent		X			
Pretest survey including all		X			

outcome  
measures

Randomization		X			
Control & experimental interventions			X		
Posttest survey				X	
1-month follow- up survey					X
Adverse event reporting	X	X	X	X	X

## 2 INTRODUCTION

### 2.1 STUDY RATIONALE

The prevalence of adolescent behaviors that can lead to obesity are alarming, and reduced life expectancy is the future of America's youth if behavioral changes are not implemented to improve health and reduce the obesity burden. Researchers have argued that health literacy is a precursor to health knowledge and is necessary for translating knowledge about healthy choices into behavior, with low health literacy being associated with reduced preventive health behaviors in adults. Given the lack of health literacy-specific interventions addressing adolescents' obesogenic behaviors, the purpose of this study is to examine the preliminary effectiveness of adding a health literacy module to an obesity prevention intervention that addresses adolescents' obesogenic behaviors.

### 2.2 BACKGROUND

The rates of pediatric obesity (~19%) and diabetes (0.24%) in the US are alarming and behaviors implicated in obesity and type 2 diabetes are highly prevalent. Approximately 69% and 73% of adolescents consume less than two fruits and vegetables daily respectively, while 53% engage in insufficient physical activity. These behaviors magnify adolescents' immediate and long-term risks for obesity and obesity-related chronic illnesses, as well as complicate the treatment of obesity-related chronic illnesses. Children and adolescents who are obese are four times more likely to be diagnosed with type 2 diabetes than normal weight children, with serious short and long-term consequences impacting quality of life. Reduced life expectancy is the future of America's youth if behavioral changes are not implemented to improve health and reduce the obesity burden. Reversing current national trends in obesity and type 2 diabetes require novel and sustainable prevention strategies to address children and adolescents' obesogenic behaviors.

Adolescence is marked by increased autonomy in decision-making, yet data suggest that adolescents are not equipped with all the skills to make effective health-related behavioral decisions. While health knowledge works in conjunction with motivation and behavioral skills to predict behavior, most existing adolescent interventions target these variables in isolation with modest success. Researchers have argued that health literacy (HL) – the ability to access, understand, and use health information to make informed health decisions – is a precursor to health knowledge and is necessary for translating health knowledge into behavior. Low HL among adults is associated with poor ability to interpret health messages, and results in reduced preventive health behaviors. Further, parent and adolescent HL is negatively related to adolescents' obesity status. Thus, while research on adding HL to existing behavior interventions to improve adolescents' obesity prevention behaviors is lacking, it is expected that the inclusion of HL into existing interventions will increase intervention effectiveness and positive behavior outcomes.

The long-term goal of this line of research is to reduce the incidence of obesity in adolescents and by extension reduce the risk for obesity-related chronic illnesses using interventions that address individual

and contextual factors related to long-term health decision-making and behavior change. The goal of the proposed study is to examine the effect of adding a HL component to an obesity prevention intervention that addresses adolescents' obesogenic behavior-related health knowledge, motivation, and behavioral skills. The central hypothesis is adolescents receiving HL training as part of an obesity prevention intervention will have higher rates of prevention behaviors than those in the obesity prevention only condition.

## 2.3 RISK/BENEFIT ASSESSMENT

### 2.3.1 KNOWN POTENTIAL RISKS

Potential risk is primarily breach of confidentiality for low risk personal information such as participants' discussing intervention content to non-participants. Participants may feel some discomfort answering questions about their obesogenic behaviors and health literacy. Additionally, asking about obesogenic behaviors may bring up potentially sensitive issues, such as unhealthy weight control behaviors. Participants who report unhealthy weight control behaviors will be referred to their organization's youth program officer or mental health liaison for help with these problems. As part of the informed consent and assent, we will make both parents and participants aware of the purpose of the evaluation, the minimal risks described above, and make it clear that participation is voluntary.

### 2.3.2 KNOWN POTENTIAL BENEFITS

Potential direct benefits to all participants include education on health literacy and obesity-related health information, motivation, and behavioral skills. Specifically, participants will be provided with tools for improving health literacy and obesogenic behaviors. Indirect benefits include increased understanding of health literacy and obesogenic behaviors in adolescents can lead to more targeted interventions and health education in community settings.

### 2.3.3 ASSESSMENT OF POTENTIAL RISKS AND BENEFITS

The risks associated with participating in this study are no more than what an adolescent may experience in their daily lives. The benefits to be gained from attaining a better understanding of adolescents' health literacy and obesity-related health information, motivation, and behavioral skills and how all of this relate to their obesogenic behaviors outweigh the risks as this can have long-term consequences on what is addressed in their health curriculum, how practitioners interact with adolescents, and ultimately influence adolescents' risks for obesity and obesity-related diseases in adulthood.

## 4 STUDY DESIGN

### 4.1 OVERALL DESIGN

This is a two-arm pilot randomized control trial. Intervention conditions include (1) obesity prevention intervention without a health literacy component and (2) obesity prevention intervention with a health literacy component. This design answers the research question: “does adding a health literacy component to an obesity prevention intervention improve behavioral outcomes more than an obesity prevention intervention without a health literacy component?”

### 4.2 SCIENTIFIC RATIONALE FOR STUDY DESIGN

This study design will allow for determining the preliminary efficacy of the intervention and the results will be used to calculate power for a full-scale trial.

### 4.3 JUSTIFICATION FOR INTERVENTION

Approximately 95% of adolescents own or have access to a smartphone and ~45% are online almost constantly. Approximately 88% of adolescents have access to a computer at home. All US libraries have public-use computers with internet connectivity and 98% offer free public Wi-Fi access. These data support internet-based (eHealth) platforms for developing tools and interventions to promote health behavior change and improve adolescents’ health outcomes. EHealth interventions targeting health behavior change have increased dramatically over the last 10-20 years and eHealth interventions addressing obesity in adolescents have had favorable outcomes on reducing body mass index and improving PA and diet.

Methods for intervention delivery: The intervention will be delivered in a digital online format. This study will use the DeLP platform to deliver the intervention.

Description of Digital Platform. Created by 3C Institute, DeLP, is an online platform that uses evidence-based cognitive theory of multimedia learning to engage diverse types of online learners. The platform allows each online module to contain a mix of didactic instructions with self-assessments, demonstration videos, and interactive practice activities to apply learned skills (e.g., mini-games, second life-inspired role playing). DeLP integrates cognitive learning principles through active engagement and use of multiple sensory modalities, both of which are implicated in enhanced user engagement, learning and memory. Research has consistently supported DeLP's high quality (e.g., ratings of quality, appeal, and engagement), value (e.g., ratings of value, innovation, and likely impact), and ease of use (e.g., ratings of usability, feasibility, and acceptability in real-world settings), in addition to DeLP's ability to achieve learning objectives. Further, DeLP is built on HTML5 web standards accessible through any modern web browser and smartphone with no extra software, hardware, or technical expertise needed.

The intervention uses multiple instructional styles (e.g., illustrative role plays) and interactive elements (e.g., self-assessments, mini-games, drag-and-drops) to facilitate learning and memory of intervention content and maintain user engagement.

#### 4.4 END-OF-STUDY DEFINITION

A participant is considered to have completed the study if he or she has completed the pretest assessments, all intervention modules, posttest assessments, and 1-month follow-up assessments. The end of the study is defined as completion of the 1-month follow-up assessment.

## 5 STUDY POPULATION

### 5.1 INCLUSION CRITERIA

Adolescents 13-16 years old at time of enrollment (may turn age 17 during the study)  
Must have parental consent  
All weight classifications

### 5.2 EXCLUSION CRITERIA

Adolescents younger than 13 years or older than 16 years at time of enrollment  
No parental consent  
Medical conditions preventing engagement in physical activity  
Medical conditions resulting in extremely restricted diets (e.g., ketogenic diet)  
Already participating in an intervention related to healthy eating, physical activity and/or obesity prevention or treatment

### 5.3 SCREEN FAILURES

Screen failures are defined as participants who consent/assent to participate in this study but are not subsequently assigned to the study intervention or entered in the study. Individuals who do not meet the criteria for participation in this trial (screen failure) because of meeting one or more exclusion criteria that are likely to change over time may be rescreened. Screen failures will be notified that they are not eligible for the study and asked if they would like to be considered for future studies.

### 5.4 STRATEGIES FOR RECRUITMENT AND RETENTION

#### Recruitment

Study flyers will be posted in public areas at each site, announcements will be made at youth events, and study staff will table at community sites.

#### Retention

One of the advantages of a digital intervention is that it decreases the travel and time burdens as individuals may complete the modules based on their individual schedules. While adolescents may not prioritize the intervention or forget about it given the lack of deadline, the intervention will have a built-in point system to immediately incentivize data collection and module completion. For example, participants will be provided with a suggested schedule for completing the modules and will receive email and text prompts encouraging them to log in and complete the module prior to the scheduled date. They will be incentivized through the point system for completing the module early and according

to the schedule. Participants will also be incentivized through the point system to complete each module in one sitting to facilitate making connections across the module. Though participants will receive gift cards at each data collection completion, they will also receive points for completing data collections. These points may be redeemed for prizes at the end of the study through the points store where more desirable prizes will require more points. Collecting biometric data at posttest and follow-up may be difficult given that all other data collection will occur online. Bonus incentives for completing all aspects of the study (intervention and all data collection) should further motivate participants to maintain involvement in the project. The use of email and text prompts throughout the study should also encourage retention. We plan to collect multiple phone numbers and email address for participants and their parents to be able to reach them in the event of lost devices or changes in phone numbers or email addresses.

## 6 STUDY INTERVENTION(S) OR EXPERIMENTAL MANIPULATION(S)

### 6.1 STUDY INTERVENTION(S) OR EXPERIMENTAL MANIPULATION(S) ADMINISTRATION

#### 6.1.1 STUDY INTERVENTION OR EXPERIMENTAL MANIPULATION DESCRIPTION

##### **Comparison Arm: Vaping and Obesity Prevention Only**

**Arm Description:** Obesity prevention and vaping

##### Module 1. Introduction

- Introduction to the intervention and orientation for using the web platform
- Initial goal setting

##### Module 2. Vaping

- Factual information about vaping devices and vaping
- Beliefs and attitudes about nicotine products
- Refusing and avoiding vaping
- Recognizing addiction and getting help

##### Module 3. Health information

- Factual information about healthy eating and activity (PA)

##### Module 4. Motivation

- Personal: Create positive attitudes toward engagement in healthy eating and PA
- Social: Enlisting social support to increase healthy eating and PA
- Social: Identification of community resources that promote and support healthy eating and PA

##### Module 5. Behavioral Skills

- Tips for engaging in prevention behaviors and avoiding risk behaviors in the context of existing barriers
- Skills for social situations around behaviors
- Skills for making behavior part of routine
- Build autonomy, self-efficacy and model good health decision-making for health behaviors

##### **Experimental Arm: Health Literacy and Obesity Prevention**

**Arm Description:** Obesity prevention and health literacy (HL).

##### Module 1. Introduction

- Introduction to the intervention and orientation for using the web platform
- Initial goal setting

##### Module 2. Health Literacy

- Functional HL: skills for reading/understanding nutrition labels and medication instructions
- Interactive HL: verbal skills for interacting with others on health issues
- Critical HL: connections between advocacy and health
- Media HL: skills for accessing and identifying reliable source of media

##### Module 3. Health information

- Factual information about healthy eating and activity (PA)

##### Module 4. Motivation

- Personal: Create positive attitudes toward engagement in healthy eating and PA

- Social: Enlisting social support to increase healthy eating and PA
- Social: Identification of community resources that promote and support healthy eating and PA

#### Module 5. Behavioral Skills

- Tips for engaging in prevention behaviors and avoiding risk behaviors in the context of existing barriers
- Skills for social situations around behaviors
- Skills for making behavior part of routine
- Build autonomy, self-efficacy and model good health decision-making for health behaviors

---

#### 6.1.2 ADMINISTRATION AND/OR DOSING

The intervention will be administered through an interactive web-based platform. The intervention will not be proctored, rather participants may complete modules at their convenience. However, they will be provided with a suggested schedule for completing the modules. In addition to an introductory module (i.e., what is the program, instructions of navigating the website, introduction to actors, and goal setting task), the intervention includes 4 modules with 3-4 lessons per module. Lessons range from approximately 12-20 minutes long. User metrics (e.g., number of times viewed, length of time spent on page/activity) will be monitored to assess dosing.

### 6.2 FIDELITY

---

#### 6.2.1 INTERVENTIONIST TRAINING AND TRACKING

Fidelity will be assessed by monitoring user metrics including percent of video played and length of time spent on activity (vs. predicted length of time for activity completion). No interventionist training is required as the intervention is administered through a pre-programmed digital platform and is self-paced.

### 6.3 MEASURES TO MINIMIZE BIAS: RANDOMIZATION AND BLINDING

Masking is not applicable to the study design. Participants will be randomized to conditions upon enrollment with the goal of balancing the number of participants in each condition (e.g., 1st participant assigned to condition 1, 2nd to condition 2, 3rd to condition 1).

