## 10 SUPPORTING DOCUMENTATION AND OPERATIONAL CONSIDERATIONS

### 10.1 REGULATORY, ETHICAL, AND STUDY OVERSIGHT CONSIDERATIONS

#### 10.1.1 INFORMED CONSENT PROCESS

Participants will be recruited from the community organizations that agree to participate in the study with the help of community organization personnel; community organization personnel will distribute information sheets and parent permission forms to parents and adolescents. Adolescents who return signed permission forms will be provided with assent forms. Adolescents with signed parent permission forms and who provide assent will be allowed to participate in the study. The permission and assent forms will be written in simple, easy to understand language and will be reviewed by the CUNY University Integrated Institutional Review Board (IRB). Parent permission forms will be provided in both English and Spanish to accommodate Hispanic parents who are non-fluent in English. Permission from parents and assent from participants will be obtained prior to any participation in the research. The trained study research assistants will explain the purpose, methods, and extent of the study to all parents in the permission form, and ask them to call the researchers with any questions before signing. The study research assistants will also explain the purpose, methods, and extent of the study to all adolescents with signed informed consent forms, and give them an opportunity to ask any questions before providing assent. In addition, study research assistants will question potential participants to confirm their understanding of the information. Research assistants will be given a structured checklist for this purpose.

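### Masking is set aside without a reason, although the analyst could be masked and participants' cues about which module is under test could be reduced; the benefit statement and comparator description also need correcting

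*Combined protocol and SAP*

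**What the plan says.** Section 6.3, which covers measures against bias, states "Masking is not applicable to the study design". It gives no reason and does not mention participants, staff or the analyst separately.

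Section 6.1.1 heads the control condition "Comparison Arm: Vaping and Obesity Prevention Only" and lists five modules for each arm. The comparison arm has "Module 2. Vaping" where the experimental arm has a health literacy module. The entries for Modules 1, 3, 4 and 5 are the same in both arms. Section 6.2.1 says the platform is pre-programmed and self-paced, with no interventionist to train.

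Section 8.1 measures the primary outcomes (diet, physical activity and sedentary behavior) by questionnaires with recall periods of 7 to 30 days for diet and 7 days for activity. It describes the secondary health literacy instruments as objective.

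Section 10.1.1 has research assistants "explain the purpose, methods, and extent of the study to all adolescents" before assent.

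Section 2.3.2 states "Potential direct benefits to all participants include education on health literacy". Sections 1.1, 4.1 and 9.1 describe the comparator as obesity prevention alone or without health literacy, and none of them mentions vaping.

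**The concern.** When outcomes are self-reported, a participant who believes they have the version expected to work may report better behavior. If that tendency differs between arms, the t-tests and chi-square tests in 9.4.1 cannot separate it from a real effect. The consequence reaches past this pilot, because 4.2 and 9.4.1 use its between-group differences and standard deviations to size the next trial.

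An unmasked analyst is a second, smaller exposure. Section 8.1 names two diet and two activity instruments, and 9.4.1 allows both continuous change and an improved/not improved split. Choices among these could be made with the arms known.

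Two wording problems lie alongside. A benefit is promised to an arm that has no module to deliver it. And the stated research question contrasts health literacy with nothing added, whereas the design contrasts it with a vaping module.

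**Working it through.** The plan states no sample size, alpha, effect size or standard deviation, so it has no figure to reproduce. The check is mainly a comparison of sections.

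**1. Could anyone be masked?**
- *Analyst.* Data arrive by electronic survey (10.1.7.1) and are scored by the test authors' guidelines (8.1). Nothing requires the analyst to know which arm is which.
- *Delivery.* It is automated (6.2.1), so no interventionist needs to know the arm.
- *Participants.* They will see their own module content, so they cannot be masked to it. They could be left untold which Module 2 is under test, because each sees a complete five-module program on the same platform.

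**2. How far could participants' awareness be reduced?** Three cues remain:
- The study title names health literacy (1.1).
- The risks disclosed at consent and assent include discomfort at questions about health literacy (2.3.1).
- The pretest contains all outcome measures and comes before the intervention (1.2). Those measures include four types of health literacy (8.1). No vaping outcome is listed.

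An alert participant could work out the hypothesis. Neutral wording weakens the cue and does not remove it.

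**3. Which outcomes are exposed?** All primary outcomes in 8.1 are questionnaire measures. Section 5.4 mentions biometric data collection, but 8.1 lists no biometric outcome. The health literacy measures, described as objective, are less exposed.

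**4. Benefit statement against arm content.** Section 2.3.2 gives health literacy education to everyone. Section 6.1.1 gives the comparison arm no health literacy module, and no section describes later access. These statements conflict.

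**5. Are the two Module 2s equal in dose?** Section 6.1.2 gives 3–4 lessons per module at about 12–20 minutes each:
- shortest module: 3 × 12 = 36 minutes
- longest module: 4 × 20 = 80 minutes
- possible difference: 80 − 36 = 44 minutes

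No duration is given for either Module 2, so equal attention is not shown.

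**6. Illustration only; every input is assumed.** Suppose there is no true effect, the change score has SD 1, the test is two-sided at 5%, and reporting differs between arms by *b* SD with *n* per arm. By the normal approximation, with z = b / √(2/n),

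P(reject) = Φ(z − 1.96) + Φ(−z − 1.96).

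For b = 0.2 and n = 20, z = 0.2 / 0.316 = 0.632, and P = Φ(−1.328) + Φ(−2.592) = 0.092 + 0.005 = 0.097.

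| n per arm | b = 0 | b = 0.1 | b = 0.2 | b = 0.3 |
|---|---|---|---|---|
| 20 | 5.0% | 6.2% | 9.7% | 15.8% |
| 30 | 5.0% | 6.7% | 12.1% | 21.3% |
| 50 | 5.0% | 7.9% | 17.0% | 32.3% |
| 100 | 5.0% | 10.9% | 29.3% | 56.4% |

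The table shows how error would grow with a differential shift. It gives no evidence that such a shift exists here.

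**The case against.** The strongest reply is that behavioral programs cannot be blinded to content, and that these arms share almost everything. Modules 3 to 5 carry the same listed healthy-eating and activity material, so pressure to report good behavior falls largely on both arms, and only a difference between them biases the comparison. That stands. It makes a large differential less likely than with a no-treatment control, but does not exclude one. It is also no argument against masking the analyst.

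It is also fair to say that coding the arms does not settle which instrument or outcome is primary. That is a matter of outcome definition and needs its own remedy.

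Several stronger readings are tempting, and the documents do not support them:
- *That participants could be fully masked to the hypothesis.* The title, the disclosed risks and the pretest battery point the other way.
- *That 2.3.2 tells the comparison arm what it is missing and so causes bias.* It is protocol text, and nothing shows that participants read it. If they were told that everyone receives health literacy education, expectations might be levelled. It is a contradiction to correct and plays no part in the bias argument.
- *That the comparator is attention-matched.* The plan does not say so and gives no Module 2 durations.
- *That the plan hides the vaping module.* Section 6.1.1 shows it openly in the arm heading, in "Arm Description: Obesity prevention and vaping" and in the module list. The other sections use incomplete shorthand.

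**Conclusion.** The point holds in limited form. Section 6.3 gives no reason for excluding masking. Analyst masking is feasible, and partial protection for participants is feasible if the IRB accepts neutral wording. That feasibility is inferred from the described format; the participant part also depends on the permission and assent wording, since the plan does not say how far arm roles are disclosed.

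The size of any differential reporting cannot be estimated from the documents and is probably limited. The exposure concerns the self-reported primary outcomes, much less the secondary measures.

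The conflict between 2.3.2 and 6.1.1 is certain and independent of masking. So is the incomplete comparator description. A difference between arms would show health literacy against vaping content on top of a shared program, and the conclusion should be worded that way.

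The allocation example in the same section, "e.g., 1st participant assigned to condition 1, 2nd to condition 2, 3rd to condition 1", is a separate matter that these changes do not address.

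**What to change.** **Section 6.3.** Replace the masking sentence with:

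> Arms carry neutral labels, and participant-facing materials describe two versions of an online health program without saying which module is under test, subject to IRB approval; participants are not masked to module content. The analyst works with codes A/B until the analysis code is final.

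For the coding to work, the analyst's file should omit Module 2 titles and module-level usage data that would reveal the arm.

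**Section 2.3.2.** List health literacy education as a benefit for the experimental arm only, or describe later access for the comparison arm. Check that the permission and assent forms agree.

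**Sections 1.1, 4.1 and 9.1.** Describe the comparator as obesity prevention plus a vaping module. Do not call it attention-matched unless the two Module 2 durations are shown to be equal.

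**Cost.** Wording changes in the protocol and participant materials, and a coded data file. The main downside is that the IRB must accept a neutral statement of purpose, possibly with debriefing after Week 12.

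### Section 6.3 calls allocation random, but the only method it gives, as an example, is alternation, and no section describes a random sequence or allocation concealment

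*Combined protocol and SAP*

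**What the plan says.** Section 4.1 sets the design: "This is a two-arm pilot randomized control trial". Section 6.3 is the only place that describes allocation. It states: "Participants will be randomized to conditions upon enrollment with the goal of balancing the number of participants in each condition". The example that follows in the same sentence is "1st participant assigned to condition 1, 2nd to condition 2, 3rd to condition 1". The same section says "Masking is not applicable to the study design".

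Other sections rely on this. Section 9.3 defines the analysis population as everyone randomised. Section 9.4.1 compares the groups at baseline to see whether randomisation produced balance, then compares changes from pretest to the 1-month follow-up by t-tests, and improved against not improved by chi-square tests. It mentions no covariate adjustment. It also uses the group differences and the standard deviations of change to size the next study.

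The Schedule of Activities (section 1.2) puts assent, the pretest survey and randomisation all in Week 2, with the randomisation row below the pretest row.

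**The concern.** Alternation has no element of chance. Once one assignment is known, so is the next. A person who knows the last assignment and has a say in who is enrolled next, or when, can influence which adolescents enter which arm, deliberately or not. Random allocation with concealment is the protection against this, and the plan describes neither.

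The consequence falls on the trial's one comparison. The tests in section 9.4.1 take the groups to be alike apart from chance and the intervention. If enrolment was selective, a difference in change at 1 month could reflect who was enrolled. Nothing in the planned analysis would absorb that, because no baseline covariates enter it. The baseline comparison covers only measured variables, so it cannot rule out imbalance on unmeasured traits, such as motivation, that predict change. A biased difference would also carry forward into the sample size of the next study.

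**Working it through.** **Inputs from the documents**

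- Sequence: 1, 2, 1, given as an example (section 6.3).
- Aim: equal numbers per arm (section 6.3), so 1:1 is implied.
- Masking: none (section 6.3).
- Sites: more than one, number not given (section 5.4: "Study flyers will be posted in public areas at each site").
- Staff contact before assignment: "community organization personnel will distribute information sheets and parent permission forms to parents and adolescents" and "The study research assistants will also explain the purpose, methods, and extent of the study to all adolescents with signed informed consent forms" (both section 10.1.1).
- Sample size, effect size, SD and alpha: none stated. Section 9.2 says no power calculation was made, so the plan has no figure of its own to reproduce.

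**Step 1. Predictability of the next assignment**

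Under alternation, with arms labelled 1 and 2, assignment k+1 equals 3 minus assignment k. Given the previous assignment, the next is known with probability 1. Under simple randomisation the probability of a correct guess is 0.5.

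For unconcealed permuted blocks, take the best simple guess: the arm with fewer so far in the block, or a coin toss if tied. For a block of 4 the chances of a correct guess by position are:

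- position 1: 1/2
- position 2: 2/3
- position 3: 2/3 × 1/2 + 1/3 × 1 = 2/3
- position 4: 1

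The mean is (0.500 + 0.667 + 0.667 + 1.000)/4 = 0.708. Assignments known with certainty, if the block size is known, are position 4 always and position 3 one time in three: (1 + 1/3)/4 = 0.333. Enumeration of the other block sizes, and simulation for mixed blocks, give:

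| Scheme, earlier assignments visible | Guessed correctly | Known with certainty |
|---|---|---|
| Alternation, one assignment known | 100% | 100% |
| Blocks of 4 | 70.8% | 33.3% |
| Blocks of 6 | 68.3% | 25.0% |
| Blocks of 8 | 66.6% | 20.0% |
| Blocks of 4 and 6, randomly mixed | about 69% | not computed |
| Simple randomisation | 50% | 0% |

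Unconcealed blocks are therefore still partly predictable. If recruiters cannot see earlier assignments, a random block list gives them no better than chance. Both parts of the repair are needed: a random sequence and concealment.

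**Step 2. What the text establishes about concealment and timing**

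No section names a generator, a list holder, or the person or system that assigns. No section says whether the count runs per site or across sites. On timing, section 6.3 places assignment at enrolment, while section 1.2 lists the pretest before randomisation in the same week. The two can be read consistently, but the text does not settle it.

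**Step 3. Illustration of what a selection shift would do (all values assumed)**

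Let selection move the analysed change score by d SDs between arms when there is no true effect, with n per arm and a nominal two-sided 5% test. Then λ = d/√(2/n), and the rejection rate is Φ(−1.96 − λ) + 1 − Φ(1.96 − λ). For n = 30 and d = 0.2: λ = 0.2/0.2582 = 0.775, and the rate is 0.003 + 0.118 = 0.121.

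| n per arm | d = 0.1 | d = 0.2 | d = 0.3 | d = 0.5 |
|---|---|---|---|---|
| 20 | 6.2% | 9.7% | 15.8% | 35.3% |
| 30 | 6.7% | 12.1% | 21.3% | 49.1% |
| 50 | 7.9% | 17.0% | 32.3% | 70.5% |

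The documents give neither n nor d, so the table shows sensitivity and estimates nothing about this trial.

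**The case against.** The strongest reply is that section 6.3 says participants will be randomised, and that the sequence is only an example, perhaps meant to show equal numbers. That is a possible reading. But no other method appears anywhere, and staff who follow the section would alternate. If true randomisation is intended, the example contradicts it. The text needs correcting on either reading.

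The second reply is that this is a feasibility pilot (section 9.2). That lessens the consequence without removing it: the objective and hypothesis are comparative (sections 1.1 and 9.1), and the differences will size the next study.

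Several stronger readings are tempting, and the documents do not support them.

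- A reader might infer that recruiters know every next assignment, or that site staff control the order of enrolment. The documents say only that community personnel hand out forms and research assistants explain the study. With one count across several sites, a local recruiter might not know the next arm. The sound statement is that nothing prevents such knowledge.
- A reader might infer that adolescents learn their arm before the pretest. The row order in section 1.2 points the other way, so this is an ambiguity to resolve.
- A reader might put a figure on the bias. If recruiters order a share f of consecutive pairs perfectly on a normally distributed trait, the arms differ by f × 2/√π = 1.128f SD: 0.11 SD at 10% and 0.23 SD at 20%. But f is invented, and the gap is on the trait. The planned analysis uses change from pretest, so a stable difference in level drops out and only traits that predict change matter. The documents give no effect size to set beside it.
- A reader might conclude that participants could easily be masked, since the arms differ only in module 2 (section 6.1.1). That is a separate question. It depends on what the permission and assent forms disclose, and those are not available here.

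**Conclusion.** The point stands and should be corrected before anyone is assigned under section 6.3 as written. It is more than missing detail: the one procedure on the page is deterministic and contradicts the label in section 4.1. If it is followed, assignments are 100% predictable from the previous one, against 50% under simple randomisation. The population of randomised participants in section 9.3 and the balance check in section 9.4.1 would then not mean what they say.

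Whether bias follows depends on facts that the documents leave open: who assigns, whether anyone involved in recruitment sees the running count, and whether enrolment order can be influenced. Its size cannot be computed from the documents. Analysis cannot reliably repair it afterwards, because imbalance on unmeasured traits would remain.

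**What to change.** In section 6.3, delete the alternation example and state the following:

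- **Sequence:** computer-generated permuted blocks with randomly varying sizes (for example 4 and 6), 1:1, stratified by site if there are several sites and numbers allow.
- **Concealment:** the list is held by the web platform or by a person independent of recruitment, and block sizes are not disclosed to recruiting staff.
- **Timing:** the assignment is released only after assent is recorded and the pretest survey is submitted. Reword the timing in section 6.3 to agree with the order in section 1.2.

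If alternation has already been used, say so and describe the trial as quasi-randomised in sections 4.1, 9.3 and 9.4.1 and in any report.

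The cost is one protocol paragraph and one list. The equal-numbers goal is kept closely: with a largest block of 6, an incomplete block leaves the arms at most 3 apart in each list, against at most 1 under alternation. Site stratification would add these gaps across sites, which is a reason to use it only if numbers allow.

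Optional and separate: keep the analyst masked to arm codes until the analysis code is final.
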